### **3.6 Unscheduled Visit**

A subject may be required to return to the clinic in the morning following a 10-hour fast for an Unscheduled Visit for a repeat measurement of fasting blood glucose and any necessary clinical safety laboratory assessments, if the investigator deems it necessary. AEs/SAEs assessment will also be performed.

### **3.7 Self-Monitoring Fasting Blood Glucose and Patient Diaries**

All patients will self-monitor fasting morning blood glucose levels three (3) times weekly during the run-in and treatment period. Monitoring must be performed at the same time each designated day ( $\pm$  10 minutes) prior any caloric intake. Patients will be required to record the values in a patient diary and bring the diary to each clinic visit. Information recorded for the fasting blood glucose will be reviewed by the clinical research coordinator for completeness and transcribed onto electronic case report form (eCRF). During the study, both fasting finger stick glucose and laboratory fasting plasma glucose will be obtained.

If a fasting blood glucose measures greater than or equal to 270 mg/dL (15 mmol/L) during daily self-monitoring or during any in-clinic visit, the patient will be required to contact the clinic to report the value. The patient may be required to return for an unscheduled visit to the clinic for a repeat measurement of fasting blood glucose within one week after the original measurement. If

the patient is invited for an unscheduled visit, blood will be drawn and sent to lab for plasma glucose determination. If the repeat measurement is also greater than or equal to 270 mg/dL, the patient will be discontinued from treatment with study drug and offered rescue medication. The patient will continue to be seen for all remaining study visits, if possible.

If a fasting blood glucose value is <70 mg/dL, the patient should drink 1 cup of orange juice or swallow 3-4 glucose tablets. The patient must check his blood sugar after 10 min and if the blood glucose level does not raise, the patient needs to drink another cup of orange juice or swallow 3-4 glucose tablets. Blood sugar must be checked again after 10 minutes. The patient must call to report this event to the study site and record all blood glucose levels in the diary.

If three or more fingerstick glucose values of <50 mg/dL (2.78 mmol/L) are observed within 12 hours subsequent to administration of study drug without a reasonable explanation (such as increased physical activity and/or skipped meal), the patient will be discontinued from treatment with study drug and rescued with glucose administration (20g of glucose tablets) which will be available at all times at the study site. This information will be recorded in the patient's diary and the patient will be instructed to contact the study site if this occurs. The patient will continue to be seen for all remaining study visits.

Sites will instruct patients to immediately perform a finger stick glucose measurement if any symptoms occur that may be related to hypoglycemia (e.g., weakness, dizziness, shakiness, increased sweating, palpitations, or confusion), and to avoid delay in treating these symptoms. The measurements will be recorded in the patient diary. Patients will always carry glucose tablets with them and ingest 3-4 tablets if hypoglycemia occurs.

Hypoglycemia and associated symptoms (e.g., weakness, dizziness, shakiness, increased sweating, palpitations, or confusion), have been associated with insulin administration, including ORMD-0801.

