Subjects will then undergo a Treatment Phase consisting of a treatment period of 12 weeks that will start at Visit 3 (Week 0) and outpatient visits at Weeks 1, 2, 4, 8, and 12 (final visit). At each visit, concomitant medication will be reviewed, weight will be measured, and sufficient quantity of medication will be dispensed to last until the next nominal clinic visit. Medication compliance check will be performed, self-monitored fasting morning blood glucose (finger-stick) will be recorded 3 days weekly in the morning and subjects' diaries will be reviewed. Vital signs (SBP/DBP, heart rate and oral temperature) will be recorded. Adverse events will be monitored and recorded. ORMD-0801 morning treatment will be administered in clinic during Visits 3, 6 and 7.

At Visit 3, urine pregnancy test will be performed for females of childbearing potential. At Visit 8, subjects will have HbA1c evaluations and MRI-PDFF performed. At Visits 3 and 8, a complete physical exam and CAP-Fibroscan will be performed.

At Visits 3 (baseline), 6, 7, and 8, patients will have clinical laboratory evaluations (serum chemistry, hematology) and blood lipids performed. Fasting blood glucose, insulin (also used for HOMA estimates) and adiponectin levels will be measured.

The End-of-Study (EOS) Visit (Visit 9) will be conducted 4 weeks following the last scheduled treatment visit. Subjects concomitant medications will be reviewed, and weight will be measured. A complete physical exam and ECG will be performed and vital signs (SBP/DBP, heart rate and oral temperature) will be measured if deemed necessary by the investigator. Clinical laboratory evaluations [serum chemistry (including liver function tests (LFTs) and blood lipids) and hematology] will be performed. Fasting blood glucose, fasting insulin, HbA1c and adiponectin levels will be measured. Subject diaries will be collected and reviewed for self-monitored fasting morning blood glucose. Adverse events will be monitored and recorded. Subjects who are discontinued early from the study will complete the EOS evaluations at the time of early discontinuation.

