## 7 ADVERSE EVENTS AND SAFETY REPORTING

Information about all adverse events, whether volunteered by the patient, discovered by Investigator questioning, or detected through physical examination, laboratory test or other means, will be collected and recorded on the Adverse Event Case Report Form and followed-up as appropriate.

Medical conditions present at study entry are considered pre-existing conditions and will be documented as medical history in the study source and eCRF documents. All adverse events, including worsening of pre-existing conditions, must be reported and documented as described below.

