### 7.3 Adverse Events of Special Interest

#### 7.3.1 Adverse Events of Hypoglycemia

The CTCAE (version 5.0) criteria for mild, moderate, and severe hypoglycemia based on blood glucose will be used, as shown below:

Mild: < 70 – 55 mg/dL (< 3.8 - 3.0 mmol/L)

Moderate: < 55 – 40 mg/dL (< 3.0 - 2.2 mmol/L)

Severe: < 40 – 30 mg/dL (< 2.2 - 1.7 mmol/L)

Life Threatening: < 30 mg/dL (< 1.7 mmol/L)

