## 7.5 Recording Adverse Events

All adverse events experienced during the trial, regardless of relationship to study medication, must be recorded on the Adverse Event eCRF from the time of patient consent until completion of patients End-of-Study Visit (Visit 9). All serious adverse events will be collected through Visit 9. The Investigator must continue to follow all non-serious events possibly related to the study medication and all serious adverse events until they resolve or until the Investigator assesses them in writing as chronic or stable.

Regardless of relationship to study medication, the event must be recorded on the Adverse Event eCRF. Adverse event documentation should include the following information:

- Standard medical terminology for the AE
- Description of adverse event
- Date and time of onset
- Date and time of resolution of the adverse event
- Whether or not the event is ongoing
- Severity of the event
- Relationship between the adverse event and the investigational product
- Description of any actions taken (e.g., medications, treatments)
- Outcome of the AE
- Whether or not the effect was serious and/or unanticipated

Whenever possible, a diagnosis should be given when signs and symptoms are due to common etiology (e.g., cough, runny nose, sneezing, sore throat, and head congestion should be reported as "upper respiratory infection"). For the purposes of this study, hypoglycemic events will be considered adverse events and should be recorded in source and eCRF records.

When a diagnosis is not available, each adverse event should be reported separately. For example, "nausea and vomiting" should be split into two separate events.

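### Hypoglycemia incidence can under-count low glucose values already in the database: no step matches diary values to AE entries, and no by-arm count is derived from glucose

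*Combined protocol and SAP*

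**What the plan says.** **How events are defined.** Sections 2.1 and 2.3 make safety the primary objective and endpoint, and the synopsis names hypoglycemia within the safety assessments. It is the only entry under adverse events of special interest. Section 7.3.1 says the CTCAE "criteria for mild, moderate, and severe hypoglycemia based on blood glucose will be used, as shown below", with grades starting below 70, 55, 40 and 30 mg/dL.

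**How glucose is collected.** Section 3.7: "All patients will self-monitor fasting morning blood glucose levels three (3) times weekly during the run-in and treatment period". The diary information "will be reviewed by the clinical research coordinator for completeness and transcribed onto electronic case report form (eCRF". For a fasting value below 70 mg/dL, "The patient must call to report this event to the study site and record all blood glucose levels in the diary". In the treatment phase, Section 3.1 has readings recorded "3 days weekly in the morning and subjects' diaries will be reviewed".

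**How AEs are recorded.** Section 7 covers events "detected through physical examination, laboratory test or other means, will be collected and recorded on the Adverse Event Case Report Form". Section 7.5 adds that "hypoglycemic events will be considered adverse events and should be recorded in source and eCRF records".

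**What is reported.** Section 8.2.1 tabulates TEAE incidence as numbers and percentages of subjects, built from AE entries. Section 8.2.2 lists and summarizes the laboratory panels, with shift tables. Sections 8.2.1 to 8.2.6 name neither a hypoglycemia table nor a self-monitored glucose summary. Section 8.2.7 then makes a general promise to list and describe all data. Section 8 opens by deferring further detail to a SAP, and the document under review contains no separate SAP text.

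**The concern.** For its main expected harm the plan has an objective definition, a glucose value, and collects that value several times a week. Yet the only incidence count it names rests on a different record, the AE page. The two agree only if someone at the site notices each low value and enters it. The plan does not say who compares diary values with 70 mg/dL, or that anyone checks afterwards that low values and AE entries agree.

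The trial runs at five sites in two countries (Section 8.1). Nothing in Section 7.5 ties AE entry to the Section 7.3.1 limits, so one site could enter an asymptomatic reading of 65 mg/dL and another could leave it out. At stake is the hypoglycemia incidence in a small trial whose primary endpoint is safety: it may partly reflect site habits in entering AEs and fall short of what the collected glucose data show.

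**Working it through.** The plan states no figure on this point, so there is none to reproduce. The check follows a diary value through the plan, then counts the readings affected.

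**Path of a diary value below 70 mg/dL**

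| Step | Section | What is stated | Compares value with 7.3.1 limits, or with AE page? |
|---|---|---|---|
| Patient acts on the value | 3.7 | Calls site, writes values in diary | Patient applies the 70 mg/dL limit; no AE entry step stated |
| Coordinator review and transcription | 3.7 | Completeness | No |
| Visit | 3.1, 3.4.1 to 3.5, Table 1 | Diary review and AE assessment | Possible in practice, not stated |
| AE recording | 7, 7.5 | Events found by any means; hypoglycemic events are AEs | Duty stated, no value-based trigger |
| Data cleaning | 9.1.1, 9.2 | Programmed and manual checks; full review of key safety variables | No such check named |
| Incidence table | 8.2.1 | Counts AE entries | No |
| General output | 8.2.7 | Listings and descriptive statistics | Value is shown, not counted against limits |

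A low value that becomes an AE entry reaches the incidence table. One that does not reaches a listing and contributes to a mean or median. Neither output gives the number of subjects per arm below a limit.

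**Scheduled on-treatment diary readings**

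Inputs: 3 readings per week (3.7), 12 treatment weeks (3.1), about 36 subjects randomized 2:1 (5.2), about 30 completers (8.1).

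- Per subject: 3 × 12 = 36.
- Arms: 36 × 2/3 = 24 active, 36 × 1/3 = 12 placebo.
- All subjects: 36 × 36 = 1,296. Active: 24 × 36 = 864. Placebo: 12 × 36 = 432.
- If only 30 subjects (20 and 10) contribute: 30 × 36 = 1,080.

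These are all scheduled readings, not low ones. The run-in adds 3 × 2 = 6 per subject, but it precedes randomized treatment and does not bear on TEAEs.

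**Illustration only.** The documents give neither the share of subjects with a low value (*p*) nor the share of those subjects with at least one low entered as an AE (*c*). Both are assumptions here. The expected number of active subjects in the TEAE table is 24 × *p* × *c*, and the chance that the table shows none is (1 − *p* × *c*)^24.

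| *p* | Expected, *c* = 1 | Expected, *c* = 0.5 | Chance of none, *c* = 1 | Chance of none, *c* = 0.5 |
|---|---|---|---|---|
| 0.1 | 2.4 | 1.2 | 0.080 | 0.292 |
| 0.2 | 4.8 | 2.4 | 0.005 | 0.080 |
| 0.3 | 7.2 | 3.6 | 0.000 | 0.020 |

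With 24 active subjects, losing one or two entries changes the table visibly. This does not show that any are lost.

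**The case against.** The plan has more safeguards than the transcription step suggests, and several stronger readings fail because of them.

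- *Diary glucose has no planned output.* A reader who stops at Section 8.2.6 might infer this. Section 8.2.7 sits under the safety evaluation and promises listings and descriptive statistics for all data, and the synopsis promises summaries of each evaluable safety parameter. A low value in the eCRF would appear in a listing.
- *An event counts only if the patient telephones.* The documents do not support this either. Diaries are reviewed and AEs assessed at treatment visits, Section 7 takes events found by any means, and Section 7.5 requires hypoglycemic events to be recorded whether or not the patient called.
- *Asymptomatic lows are the ones left unreported.* The duty to call in Section 3.7 is set off by the value, not by symptoms, so it applies to them equally.
- *Nothing is checked after transcription.* Sections 9.1.1, 9.2 and 12.1 describe data checks, a full review of key safety variables, and comparison of eCRF with source.

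The study is also exploratory, unpowered, and plans no inferential AE comparison. A later SAP might supply the detail.

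All of this stands, and it narrows the point. What remains is that none of these provisions names a match between low values and AE entries, and a listing or a mean is not a count of subjects below a limit. General data checks may include such a query, but the plan does not commit to one.

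**Conclusion.** The point holds in a limited form. Hypoglycemia is graded by glucose value but counted by AE entry, with no stated reconciliation between the two and no by-arm count from the values. A value below 70 mg/dL that is never entered as an AE is missing from the TEAE incidence tables, though it would be listed. TEAE incidence can therefore under-count lows already in the database.

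The size is unknown. The 1,296 scheduled on-treatment readings (864 active) show how much data lacks a threshold-based summary, and assume that all 36 subjects complete every reading. They do not measure missed events. A reader might infer that some definite share of episodes is lost, or that the active arm is favored. The documents give no event rate, no rate of AE entry and no difference in entry between arms, so neither inference can be drawn. Equal under-entry in both arms would lower both incidences and shrink the absolute difference. Where a subject has several lows, subject-level incidence suffers less than an episode count.

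The change is worth making because this is the key safety signal under the primary endpoint and most of the data are already collected.

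**What to change.** 1. **Table.** In Section 8.2.1, add a program-derived table by treatment arm: number and percentage of subjects with at least one post-randomization glucose value in the eCRF below 70, 55, 40 and 30 mg/dL, the limits already in Section 7.3.1. Use diary fasting and laboratory values. Start after the first dose at Visit 3, so that the window agrees with the TEAE definition; the Visit 3 laboratory sample is drawn before dosing and falls outside it. Keep the TEAE table alongside.
2. **Edit check.** Before database lock, query every value below 70 mg/dL with no matching hypoglycemia AE (for example, same subject and date). The site then enters the event or documents why none applies.
3. **Symptom-driven readings.** Section 3.7 sends these to the diary but states transcription only for fasting values. Include them in the table and the check only after confirming that the eCRF captures them. If it does not, adding them means new data capture.

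The cost is one extra table and a few more queries. For fasting and laboratory values no new data are needed.

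### Section 3.7 starts low-glucose treatment at a level (<70 mg/dL) but repeats it only if glucose has not risen, and attaches no action to the second check

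*Combined protocol and SAP*

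**What the plan says.** The low-glucose instructions are in section 3.7.

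- **Start of treatment:** "If a fasting blood glucose value is <70 mg/dL, the patient should drink 1 cup of orange juice or swallow 3-4 glucose tablets".
- **First recheck, after 10 minutes:** "if the blood glucose level does not raise, the patient needs to drink another cup of orange juice or swallow 3-4 glucose tablets".
- **Second check:** "Blood sugar must be checked again after 10 minutes". No glucose value and no treatment go with it.
- **Call and diary:** "The patient must call to report this event to the study site and record all blood glucose levels in the diary".

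The same section then adds three provisions.

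- **Stopping and rescue rule:** "If three or more fingerstick glucose values of <50 mg/dL (2.78 mmol/L) are observed within 12 hours subsequent to administration of study drug", and there is no reasonable explanation such as exercise or a missed meal, study drug is stopped and the patient is "rescued with glucose administration (20g of glucose tablets) which will be available at all times at the study site".
- **Symptoms:** sites tell patients to test at once if symptoms suggest hypoglycemia and not to delay treating them.
- **General instruction:** patients carry glucose tablets and take 3-4 of them if hypoglycemia occurs.

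Section 7.3.1 grades hypoglycemia as an adverse event for any value below 70 mg/dL. The mild band is below 70 to 55, and the moderate band is below 55 to 40.

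**The concern.** The first dose is triggered by a level and the repeat dose by a direction. These are different tests. A patient can pass the second (glucose has gone up) while still failing the first (glucose is below 70 mg/dL). The sequence also ends with a measurement that leads to nothing.

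What is at stake is the handling of the risk this trial most expects. Safety is the primary objective. Hypoglycemia is the only adverse event of special interest in section 7.3, and sections 3.7 and 7.6.1 both associate it with the study drug. Subjects take a dose each evening before the fasting morning reading, and section 5.4 plans no dose modification. The instruction is carried out by a patient, usually alone, who may be mildly impaired at the time. It should work when read literally.

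**Working it through.** No calculation in the plan bears on this point, so the check is to follow the steps as written and ask at each one what the patient is told to do. All glucose values in the examples are assumed for illustration. They are not trial data.

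| Step | Trigger in section 3.7 | Directed treatment |
|---|---|---|
| First reading | Level: <70 mg/dL | Juice or 3-4 tablets |
| Recheck at 10 min | Direction: has not risen | Second dose |
| Second check, 10 min later | None | None |

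**Path A: rises but stays low.** First reading 45 mg/dL, recheck 50 mg/dL. The level has risen, so the recheck step does not call for a second dose. Yet 50 is below the 70 mg/dL that started treatment, and it lies in the moderate band of section 7.3.1. At most one of the first two readings is below 50 mg/dL, so the three-value rule is not met.

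**Path B: does not rise.** First reading 60, recheck 60 (second dose taken), second check 60 mg/dL. The sequence gives no further treatment. No value is below 50 mg/dL, so the three-value rule is not met here either.

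**Path C: very low and rising slowly.** First reading 42, recheck 45 mg/dL. Again no second dose is called for by the recheck step. If the second check is also below 50 mg/dL, the three-value rule could apply, provided the readings fall within 12 hours of study drug and have no reasonable explanation. That covers part of the gap.

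**The second check.** It is not clear whether it applies to everyone or only to patients who took a second dose. Under the first reading it has no action. Under the second, a patient on Path A has no second check at all. The gap exists under both.

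**Can another provision supply the missing step?**

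- *Site call.* It is required, but its stated purpose is to report the event. No time limit is given and no treatment is tied to it.
- *Symptom instruction.* It prompts testing and treatment when symptoms are present. A routine finger-stick can be low without them.
- *General tablet instruction.* Read with the <70 mg/dL limit of section 7.3.1, it can reasonably cover a patient still at 45 or 50 mg/dL. But it names no cut-off, recheck or repeat, and section 7.3.1 is an adverse event grading table rather than a patient instruction.
- *Three values below 50 mg/dL.* It is conditional, as above, and does not address a patient who stays between 50 and 69 mg/dL.

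Each provision helps. None says to recheck and re-dose until glucose is back to 70 mg/dL or above.

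**The case against.** The strongest case against is that a sensible reader would get this right. A clinician may take the recheck clause to mean a failure to recover to 70 mg/dL, or apply the opening <70 mg/dL sentence afresh to every reading. The general tablet instruction and the symptom instruction then add to the sequence. Once the site is told, the investigator can arrange an unscheduled visit (section 3.6), withdraw the subject for an adverse event (section 4.3), or treat an emergency by community standards (section 5.7). The readings come before breakfast, so a meal ordinarily follows. The diary wording and site training that patients actually receive are not in the documents.

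Much of this stands, and it limits what can be claimed. Four stronger readings are tempting and not supported.

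- *That section 3.7 contradicts itself.* It does not. The recheck step says when a second dose is required; it never tells a rising but still-low patient to refrain. Its instructions are cumulative.
- *That still-low patients are left without direction.* They are not; they have the general tablet instruction and the call.
- *That the high-glucose rule proves a drafting error, because it restates its level at the repeat ("If the repeat measurement is also greater than or equal to 270 mg/dL, the patient will be discontinued from treatment with study drug").* That rule governs stopping study drug, on a repeat taken up to a week later. It is not a first-aid step, so the comparison shows little.
- *That the gap biases the comparison of arms.* The same instruction applies to both blinded arms, section 8.2.1 plans no inferential comparison of adverse events, and nothing in the documents links it to the MRI-PDFF result.

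What remains is that the correct action has to be inferred from several sentences when one could state it.

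**Conclusion.** The point holds as a gap in the patient-safety instructions. The stepwise rule in section 3.7 does not direct re-treatment of a patient who has risen but is still below 70 mg/dL, or of one who is still low after a second dose. The surrounding provisions reduce the gap without supplying a level-based repeat step.

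Its size cannot be given as a number: the documents contain no rate of low readings or of slow recovery. Confidence in the reading of the text is high. Confidence in the practical consequence is lower, because it depends on diary wording and site instructions that are not available here. The change is recommended because it is specific and nearly free, not because harm has been shown. Sample size, error rates and the efficacy analysis are unaffected.

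**What to change.** In section 3.7:

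1. Replace the condition for the repeat dose with: *if the blood glucose level is still <70 mg/dL*.
2. State that the check and the dose are repeated every 10 minutes until the level is >=70 mg/dL. Adding only one more dose at the second check would leave that dose unchecked and move the open end one step later.
3. State that if the level is still <70 mg/dL at the second check, the patient calls the study site immediately. The call is already required; this gives it a time.
4. Make the patient diary text match.

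The cost is one changed clause, two short sentences and the diary edit, submitted as an amendment under section 10. No visit, procedure or subject is added. The downside is a few extra finger-sticks and glucose doses in patients who recover slowly.

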### 4.3 Subject and Trial Discontinuation

Subjects may choose to withdraw from this study at any time for any reason without penalty of jeopardizing their health care or loss of benefits to which the subject is otherwise entitled.

Within the provisions of informed consent and good clinical judgment with respect to safety, every attempt will be made to have subjects complete the study. The following are reasons to terminate a subject's participation in the study:

1. Subject experiences an AE that in the judgement of the Investigator poses a significant risk to the subject for continued participation in the study.
2. Subject uses any medication that in the judgment of the Investigator poses a significant risk to the subject for continued participation in the study or that will interfere with the interpretation of the results of the study.
3. Subject becomes pregnant.
4. Significant protocol violation or noncompliance on the part of the subject or the Investigator.
5. Intercurrent illness that requires treatment that is not consistent with the protocol requirements, or intercurrent illness or the associated treatment that in the judgment of the Investigator poses a significant risk to the subject for continued participation in the study.
6. Subject wishes to withdraw for any reason.
7. Sponsor elects to end the study, or the Investigational Site elects to end the study at their site.
8. Any other reason that in the judgment of the Investigator poses unacceptable risk to the subject.

Subjects who withdraw from the study prior to treatment may be replaced. Subjects who are withdrawn and have received at least one treatment will not be replaced. Subjects who discontinue study drug treatment will not be replaced.

Except in cases of emergency, the Investigator should consult with the Sponsor and the Medical Monitor before removing the subject from the study. In some circumstances it may be necessary to temporarily interrupt treatment as a result of AEs that may have an unclear relationship to the IMP. The Investigator should obtain approval from the Sponsor and Medical Monitor before restarting IMPs that were temporarily discontinued for an AE.

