If either of the criteria listed below is met, enrollment of new subjects and dosing of ongoing subjects will be temporarily stopped. The Investigator, Sponsor, and the Medical Monitor will discuss whether a lower dose or any additional treatment guidelines should be implemented, or if the trial should be permanently stopped. Any proposed changes to the protocol to address such findings will be submitted for review and approval by the IRB and U.S. Food and Drug Administration (FDA) prior to re-starting the trial.

1. A death within 30 days after IMP administration where there is a reasonable possibility that the drug caused the event;
2. Two Grade 4 AEs where there is a reasonable possibility that the IMP caused the events.

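### The Section 3.7 hypoglycemia stop counts low readings and ignores their depth, so a single fingerstick below 30 mg/dL does not make interruption of study drug mandatory for that subject

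*Combined protocol and SAP*

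**What the plan says.** Section 3.7 sets the individual stopping rule for low glucose: "If three or more fingerstick glucose values of <50 mg/dL (2.78 mmol/L) are observed within 12 hours subsequent to administration of study drug", with an exception where exercise, a missed meal or something similar explains the values. A subject who meets it stops study drug but stays in follow-up: "The patient will continue to be seen for all remaining study visits".

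For a fasting value below 70 mg/dL, Section 3.7 orders juice or glucose tablets and a recheck after 10 minutes, then says "Blood sugar must be checked again after 10 minutes". It adds "The patient must call to report this event to the study site and record all blood glucose levels in the diary". For symptoms that suggest hypoglycemia, it orders an immediate fingerstick, prompt treatment and a diary entry. It orders no call to the site for that reading unless the three-value rule is met.

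Section 7.3.1 grades hypoglycemia by glucose value, and its lowest band is "Life Threatening: < 30 mg/dL (< 1.7 mmol/L". No dosing instruction is tied to any band.

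Section 4.3 adds three provisions. Item 1 allows a subject's participation to be ended when "Subject experiences an AE that in the judgement of the Investigator poses a significant risk to the subject for continued participation in the study", and item 8 extends this to any other risk the Investigator finds unacceptable. Temporary interruption for an adverse event is possible, and then "The Investigator should obtain approval from the Sponsor and Medical Monitor before restarting IMPs that were temporarily discontinued for an AE". Enrollment and all ongoing dosing pause after a death reasonably attributable to drug, or after "Two Grade 4 AEs where there is a reasonable possibility that the IMP caused the events".

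**The concern.** Safety is the primary endpoint (Section 2.3), and hypoglycemia is the only adverse event of special interest listed (Section 7.3). The fixed rule nevertheless responds to how often glucose is low and not to how low it is. A run of readings in the Moderate band of Section 7.3.1 ends treatment automatically, while one reading in the Life Threatening band leads to no automatic action on dosing.

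What is at stake is the next dose. Dosing is twice daily, so a subject who records a value below 30 mg/dL in the morning has a night dose due between 8 PM and midnight the same day. The morning dose may also still be due, since it is allowed until 10 AM. That is less certain, because the bar in Section 5.8 on food before dosing could be read as displacing it once juice has been taken. Section 3.7 does not say to hold either dose.

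**Working it through.** **Inputs.** Section 3.7: three or more values, below 50 mg/dL (2.78 mmol/L), within 12 hours of a dose, unexplained. Section 7.3.1: Moderate is 40 to below 55 mg/dL; Life Threatening is below 30 mg/dL (1.7 mmol/L). Sections 3.1 and 5.2: about 36 subjects randomized 2:1.

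**Unit check.** mmol/L = mg/dL ÷ 18. 50 ÷ 18 = 2.78 and 30 ÷ 18 = 1.67, stated as 1.7. Both agree with the protocol.

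**Rules compared.** Current: stop if the number of values below 50 is at least 3. Proposed: keep that rule, and add a hold at any value below 30. All values are taken to fall within 12 hours of a dose and to be unexplained, which is the reading most favorable to a stop.

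| Readings (mg/dL) | Values below 50 | Current rule | With the added hold |
|---|---|---|---|
| 49, 49, 49 | 3 | stop | stop |
| 25 | 1 | no stop | hold |
| 25, 28 | 2 | no stop | hold |
| 28, 55 | 1 | no stop | hold |
| 28, 45, 55 | 2 | no stop | hold |
| 28, 55, then symptomatic 45, 44 | 3 | stop | hold at 28, then stop |
| 35, 35 | 2 | no stop | no stop |

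With a reasonable explanation, even 25, 25, 25 does not require the current stop.

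**Does another provision require interruption after one value below 30?**

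- *Section 4.3, items 1 and 8:* investigator judgement, with no glucose threshold.
- *Section 4.3, temporary interruption:* permitted, but not triggered by any value.
- *Section 4.3, trial pause:* mandatory, but it needs two related Grade 4 events. Section 7.3.1 gives band names without grade numbers, Section 7.7 ends at Severe, and Section 8.2.1 cites a different CTCAE version (4.03) from Section 7.3.1 (5.0). Treating the band as Grade 4 is therefore an inference.
- *Section 5.4:* no planned dose modification, and no glucose trigger added.
- *Section 7.5.2:* serious events are reported within 24 hours of the site being notified. This is a reporting duty and does not govern dosing.

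None of these makes interruption mandatory.

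**When would the site know?** After a fasting low, the ordered call informs it. A symptom-prompted, non-fasting low outside the three-value rule need only be written in the diary, which is brought to visits. Visits 6, 7 and 8 are nominally 28 days apart, so without a voluntary call up to 28 × 2 = 56 scheduled doses could pass before review.

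**Size of one false hold.** Active arm 36 × 2/3 = 24, and 1 ÷ 24 = 4.2%.

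**The case against.** The case for leaving the rule alone is reasonable. Three unexplained lows after a dose suggest a persisting drug effect, whereas 28 followed by 55 is one low that responded to glucose. Requiring repetition also matches the high-glucose rule in Section 3.7, where discontinuation needs a confirming value of 270 mg/dL or more. A single home reading may be a meter error. The deep single low is not ignored either: after a fasting value the patient treats, rechecks and calls, and the Investigator can then interrupt or end treatment.

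Two parts of the objection stand. First, a reader might infer that two values below 30 never oblige anyone to stop drug. The documents do not support that. Hypoglycemic events are adverse events (Section 7.5), so two separate, related episodes would trigger the pause in Section 4.3 if graded 4, and that pause covers the subject concerned. Two readings within one episode would probably count as one event and would not.

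Second, a reader might infer that a recheck of 50 or more after a deep low rules out the stop. It does not. Symptom-prompted fingersticks in the same 12 hours also count, as the sequence 28, 55, 45, 44 shows.

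The argument for repetition is weaker against the change proposed here. A reversible hold is not discontinuation, and confirmation or meter error can be weighed before restart. Investigator judgement also works only once the site knows, and the call is not ordered for every deep low.

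**Conclusion.** The point holds for a single value below 30 mg/dL, and for a single episode with such a value but fewer than three readings below 50. In those cases no provision makes interruption mandatory for that subject. Discretion, reporting and a conditional trial-wide pause remain, so the gap is the lack of an automatic hold and, for non-fasting lows, of an ordered call.

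The conclusion follows from the text and assumes no event rate. The documents give none, so nothing can be said about how many subjects would be affected. It would be too strong to conclude that subjects with deep lows are left without protection. The change is recommended because it is cheap and gives the deepest band at least as definite a response as three readings of 49.

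**What to change.** Add to Section 3.7: after any single fingerstick below 30 mg/dL, fasting or symptom-prompted, the patient holds study drug from the next dose and calls the site the same day. Study visits continue. Drug restarts only with the Sponsor and Medical Monitor approval already required by Section 4.3, and that decision weighs any repeat value, explanation or suspected meter error. The three-value discontinuation rule stays as it is.

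The cost is a protocol amendment with IRB approval before use (Section 10), a revised patient instruction and site retraining. No fingersticks, visits or blood draws are added. Some holds will follow spurious readings; each one in the active arm is a reversible interruption in 4.2% of that arm.
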